9.4.3 ANALYSIS OF THE SECONDARY ENDPOINT(S)

For each secondary endpoint:

- Analyses of secondary endpoints are not dependent on findings of the primary endpoint or on the results of the Williams' test performed on the primary endpoint.
- Analyses will use complete case subjects of the Intention-to-Treat (ITT) Analysis Dataset (i.e., all randomized participants with complete data on each specific secondary endpoint).

The analysis of the 16 secondary endpoints listed in Section 3, Objectives and Endpoints, endpoints will use ANCOVA for continuous endpoints, logistic regression for binary endpoints, and Poisson regression for counts. Complete case analyses will be used for each secondary endpoint, if missing data on that endpoint < 10% and multiple imputation will be used if missing data on the secondary endpoint is 10% or greater. The covariate in the continuous endpoint ANCOVA models will be the baseline value of the continuous endpoint. Sensitivity analyses include use of non-parametric and influence-reducing regression for continuous endpoints (lowess plots and robust regression) and generalized linear models with scale factor estimation to account for under- or over-dispersion for binary endpoint data (dispersion-corrected logistic regression) and count endpoint data (dispersion-corrected negative binomial regression). Each secondary endpoint in the planned table of 16 secondary endpoints will be compared across the 3 vitamin E doses vs Placebo using treatment effect estimates, 95% confidence limits, and p-values. The Benjamini-Hochberg Method will be use to adjust the presented p-values for the false discovery rate (FDR) from the 16x3=48 pairwise p-values.

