3 OBJECTIVES AND ENDPOINTS

OBJECTIVES	ENDPOINTS	JUSTIFICATION FOR ENDPOINTS
Primary		
The primary objective is to determine the minimum effective dose of vitamin E (133.4 mg, 266.8 mg, or 533.6 mg) at which measures of NAFLD are improved	Relative change in ALT at week 24 from baseline [i.e., (ALT at baseline – ALT at week 24)/ ALT at baseline]	ALT is the most accepted short term (<12 months) surrogate marker for histologic improvement in NAFLD.
Secondary		
The secondary objectives have been selected to provide further information on the minimum effective dose of vitamin E needed to improve measures of NAFLD progression, and to provide information on the post-treatment effects of vitamin E on the liver.	Proportion of patients achieving normalization* of ALT at 24 weeks Mean change in ALT from baseline to 24 weeks Mean change in AST and GGT from baseline to 24 weeks Mean change in hepatic fat determined by FibroScan® CAP score from baseline to 24 weeks Mean change in liver stiffness as assessed by FibroScan® from baseline to 24 weeks Time course and end of treatment improvement in ALT, AST, GGT, and alkaline phosphatase Time course and end of treatment improvement in C-reactive protein (serum marker of inflammation)	These endpoints were selected because they measure important co-morbidities of NAFLD and are useful for determining if vitamin E improves other features commonly associated with NAFLD. Safety and quality of life outcomes are also included.

OBJECTIVES	ENDPOINTS	JUSTIFICATION FOR ENDPOINTS
	
Time course and end of treatment improvement in change in total cholesterol, LDL cholesterol, HDL cholesterol, and serum triglycerides
 
Changes in fasting glucose levels from baseline to 24 weeks
 
Change in anthropometric measurements (weight, BMI, waist to hip ratio, waist circumference) from baseline to 24 weeks
 
Change in symptom assessment scores from baseline to 24 weeks
 
Change in frequency of CTCAE defined adverse events from baseline to 24 weeks
 
Mean change in ALT from 24 to 48 weeks (post-treatment).
 
Mean change in AST and GGT from 24 to 48 weeks (post-treatment).
 
Mean change in hepatic fat determined by FibroScan® CAP score from 24 to 48 weeks (post-treatment).
 
Mean change in liver stiffness as assessed by FibroScan® from 24 to 48 weeks (post-treatment).
	
Tertiary/Exploratory		

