9.4.9 EXPLORATORY ANALYSES

In parallel to the ANCOVA statistical methods used to compare continuous endpoints between the treatment groups for both the primary and secondary endpoints, we will compare results arising from ANOVA analysis (linear regression of 24-week change among treatment groups without adjusting for the baseline value of the continuous endpoint) will be used for exploratory analyses. Since ANCOVA and ANOVA are alternative models for “difference in difference” data as in the VEDS trial, we expect, given the randomized design, that the two methods will give similar results for the primary and secondary endpoints.

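### The secondary FDR family of 48 counts list rows rather than tests, and the three time-course rows have no stated longitudinal analysis

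*Combined protocol and SAP*

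**What the plan says.** Section 9.4.3 covers "The analysis of the 16 secondary endpoints listed in Section 3, Objectives and Endpoints" and states that these "endpoints will use ANCOVA for continuous endpoints, logistic regression for binary endpoints, and Poisson regression for counts". It adds: "The covariate in the continuous endpoint ANCOVA models will be the baseline value of the continuous endpoint". Each of the 16 "will be compared across the 3 vitamin E doses vs Placebo using treatment effect estimates, 95% confidence limits, and p-values". The Benjamini-Hochberg method is then used to "adjust the presented p-values for the false discovery rate (FDR) from the 16x3=48 pairwise p-values".

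Three of the 16 rows in section 3, repeated in section 9.1, are time-course endpoints. The first is "Time course and end of treatment improvement in ALT, AST, GGT, and alkaline phosphatase"; the other two cover C-reactive protein and four lipids. Two other rows already cover the change to week 24 in ALT, and in AST and GGT.

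Section 9.4.9 describes the parallel unadjusted model as a "linear regression of 24-week change among treatment groups without adjusting for the baseline value of the continuous endpoint". Section 9.4.3 names lowess plots, but only among the sensitivity analyses and without an estimate or test.

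**The concern.** Two things do not fit together.

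First, a baseline-adjusted ANCOVA with one p-value per dose is the only method given for a time-course endpoint. The plan does not say which visit, visits or summary forms the outcome. The values from weeks 4, 8 and 12 have no stated role in any efficacy analysis. If the analyst falls back on week 24, the enzyme row repeats endpoints that are already in the list.

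Second, the family of 48 assumes one p-value per row per dose, yet five rows name two or four measures each. The false discovery rate adjustment depends directly on the number of tests. If that number is wrong or open, the adjusted p-values are too small, or they depend on choices made after the data are seen.

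**Working it through.** **Step 1: the plan's own figure.** 16 rows x 3 doses = 48, which matches the stated "16x3=48 pairwise p-values" exactly. The 48 is therefore a count of rows.

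**Step 2: measures named in each row of section 3.**

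| Rows | Measures |
|---|---|
| ALT normalization | 1 |
| ALT change to week 24 | 1 |
| AST and GGT change to week 24 | 2 |
| CAP; stiffness, to week 24 | 1 + 1 |
| Time course: ALT, AST, GGT, alkaline phosphatase | 4 |
| Time course: C-reactive protein | 1 |
| Time course: total, LDL and HDL cholesterol, triglycerides | 4 |
| Fasting glucose | 1 |
| Weight, BMI, waist-to-hip ratio, waist | 4 |
| Symptom scores; adverse event frequency | 1 + 1 |
| ALT change, weeks 24 to 48 | 1 |
| AST and GGT change, weeks 24 to 48 | 2 |
| CAP; stiffness, weeks 24 to 48 | 1 + 1 |
| **Total** | **27** |

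Symptom scores and adverse event frequency are counted as one each (an assumption). One test per measure per dose gives 27 x 3 = 81.

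**Step 3: share of the time-course rows.** These rows hold 4 + 1 + 4 = 9 analytes. Within the 48 they receive 3 rows x 3 doses = 9 p-values; one test per analyte per dose needs 9 x 3 = 27. Separate ANCOVAs at every on-treatment visit (four visits for enzymes, two for C-reactive protein and lipids) would need (4 x 4 + 5 x 2) x 3 = 78 for these rows alone.

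**Step 4: overlap if the enzyme row is analysed at week 24.** Let Y be the week-24 value, B baseline and g the dose group. Fitting Y - B = a + tau g + beta B is the same as fitting Y = a + tau g + (beta + 1) B, so tau, its standard error and its p-value do not change. A check on simulated data gave p = 0.9457, 0.0371 and 0.0016 for the three doses, whether the outcome was change, improvement or the week-24 value. ALT, AST and GGT in the enzyme row would then repeat the separate week-24 endpoints exactly: 3 x 3 = 9 duplicates, leaving 81 - 9 = 72 distinct tests. Alkaline phosphatase, C-reactive protein and the lipids are not repeated.

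**Step 5: effect on Benjamini-Hochberg.** Section 9.4.3 states no FDR level; 5% is taken for illustration. The cutoff at rank i is 0.05 x i/m. Using m = 48 for 72 or 81 p-values loosens every cutoff by 72/48 = 1.5 or 81/48 = 1.69. The smallest p-value, for example, would be held to 0.05/48 = 0.00104 instead of 0.05/72 = 0.00069 or 0.05/81 = 0.00062.

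Duplicates also matter when m is counted correctly. If all nine week-24 ALT, AST and GGT tests are clearly significant (illustration), the next-ranked test faces 19/81 x 0.05 = 0.0117 with duplicates and 10/72 x 0.05 = 0.0069 without. Repeated enzyme results would ease the threshold for unrelated endpoints.

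**Step 6: data available for a course.** Section 8.1.4 has hepatic panels at weeks 4, 8, 12 and 24, and lipids and C-reactive protein at weeks 12 and 24. For GGT the documents disagree: the schedule in section 1.3 has it at every follow-up visit, while the visit lists in section 8.1.4 have it only at weeks 24 and 48.

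**The case against.** The strongest reply is that this is missing detail and not a mismatch. Section 9.4.3 does not say that the time-course rows use a single visit; that is inferred from the baseline-only covariate, the one p-value per dose and the 24-week wording in section 9.4.9, which belongs to the exploratory comparator. ANCOVA on a per-person summary, such as an on-treatment mean or slope, is a standard analysis of serial measurements and yields one p-value per dose. This stands: ANCOVA is not wrong in itself for these rows, but the plan names no such summary.

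The trial team could also keep 48 by using one joint test per row. That would be coherent, but no joint test is named, and an ANCOVA of AST and GGT, or of four lipids, does not give one p-value per dose.

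A reader might go further and infer any of the following. The documents do not support them.

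- *The time course is never tested.* The gap concerns the on-treatment weeks. Four rows test change from week 24 to week 48.
- *The trial cannot meet a time-course objective.* The secondary objectives in section 3 concern the minimum effective dose and post-treatment effects. Time course is endpoint wording, and the synopsis refers to patterns only for weeks 24 to 48.
- *Exact duplicates sit inside the 48.* With one p-value per row per dose, the enzyme row cannot repeat both other rows. Duplicates arise only when each analyte is tested, and the family is then no longer 48.
- *Using all visits would bring a known gain in precision.* An average over weeks 4 to 24 is a different estimand from the week-24 effect. Section 2.3.2 says that ALT improved over 3 to 6 months, so early visits may dilute the effect.

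**Conclusion.** The family size is wrong as written. Testing the listed measures gives 81 p-values, or 72 distinct ones if the enzyme row is read at week 24. A divisor of 48 would make the cutoffs 1.5 to 1.7 times too lenient. This rests on one test per named measure per dose and on the two counting assumptions in the working. The size of the error in practice depends on whether the analyst holds the divisor at 48 or enters the actual number of tests, and the plan leaves only the first as the literal reading.

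For the time-course rows the conclusion is narrower: no longitudinal analysis is specified for weeks 4 to 24, or for weeks 12 and 24 in the case of C-reactive protein and lipids. Stating one is a cheap improvement. The point should be settled before unmasking, but it does not touch the primary dose selection, which section 9.4.3 keeps separate from the secondary analyses.

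**What to change.** Keep ANCOVA for the endpoints measured at a single time. For the time-course rows, specify a repeated-measures model with treatment, visit, treatment-by-visit, baseline and baseline-by-visit terms, and one pre-specified course contrast per analyte per dose. Count week-24 ALT, AST and GGT once, in their own rows.

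Then list every test in the Benjamini-Hochberg family and replace 48 with the count:

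- One course contrast per time-course analyte: 18 other measures x 3 + 9 analytes x 3 = 54 + 27 = 81.
- With week-24 contrasts for alkaline phosphatase, C-reactive protein and the four lipids as well: 81 + 6 x 3 = 99.

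Reconcile the GGT schedule between sections 1.3 and 8.1.4 first. If GGT is drawn only at week 24 during treatment, it has no separate course and each count falls by 3.

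When choosing the course contrast, note that section 8.1.4.1 allows outside laboratories at weeks 4 and 8, while section 8.2 commits to the same laboratory for ALT only at baseline, week 24 and week 48.

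The cost is a few lines of SAP text, routine mixed-model code and a larger, slightly stricter family. No new data are needed beyond those already scheduled.

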9 STATISTICAL CONSIDERATIONS

9.1 STATISTICAL HYPOTHESES

- Primary Efficacy Endpoint(s): That one of the doses of vitamin E at 133.4 mg (200 IU), 266.8 mg (400 IU), or 533.6 mg (800 IU) daily is the minimum effective dose for improving relative change in alanine aminotransferase (ALT) from baseline to 24 weeks.
- Secondary Efficacy Endpoints(s): That one or more of vitamin E at 133.4 mg (200 IU), 266.8 mg (400 IU), or 533.6 mg (800 IU) daily is better than placebo in improving:
 - Proportion of patients achieving normalization* of ALT at 24 weeks
 - Mean change in ALT from baseline to 24 weeks
 - Mean change in AST and GGT from baseline to 24 weeks
 - Mean change in hepatic fat determined by FibroScan® CAP score from baseline to 24 weeks
 - Mean change in liver stiffness as assessed by FibroScan® from baseline to 24 weeks
 - Time course and end of treatment improvement in ALT, AST, GGT, and alkaline phosphatase
 - Time course and end of treatment improvement in C-reactive protein (serum marker of inflammation)
 - Time course and end of treatment improvement in change in total cholesterol, LDL cholesterol, HDL cholesterol, and serum triglycerides
 - Changes in fasting glucose levels from baseline to 24 weeks
 - Change in anthropometric measurements (weight, BMI, waist to hip ratio, waist circumference) from baseline to 24 weeks
 - Change in symptom assessment scores from baseline to 24 weeks
 - Change in frequency of CTCAE defined adverse events from baseline to 24 weeks
 - Mean change in ALT from 24 to 48 weeks (post-treatment).

- Mean change in AST and GGT from 24 to 48 weeks (post-treatment).
- Mean change in hepatic fat determined by FibroScan® CAP score from 24 to 48 weeks (post-treatment).
- Mean change in liver stiffness as assessed by FibroScan® from 24 to 48 weeks (post-treatment).

*Normalization of ALT is defined as a decrease in ALT to less than or equal to the ULN at the 24 week visit among participants who had an ALT value greater than ULN at baseline. Values for ULN are defined at each clinical center per institutional guidelines.

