9.4.4 SAFETY ANALYSES

Safety data will be presented by treatment group to the Data and Safety Monitoring Board during the course of the trial. Each adverse event will be displayed showing AE name per the CTCAE v5.0 when applicable, class, severity, patient ID, clinic, treatment group, time since randomization, resolution status and physician's assessment of relatedness to treatment. Patient-specific summary tables including any adverse event (yes vs no), frequency of multiple adverse events (i.e., 0, 1, 2, 3+) and highest severity of adverse event (none, mild, moderate, severe, life-threatening) will be displayed by treatment group along with p-values from Fisher's exact tests.

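### The main analysis of count endpoints is plain Poisson, with over-dispersion corrected only in a sensitivity analysis and no rule for which result stands

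*Combined protocol and SAP*

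**What the plan says.** Section 9.4.3 assigns a main model to each type of secondary endpoint: ANCOVA for continuous endpoints, then "logistic regression for binary endpoints, and Poisson regression for counts". Among the sensitivity analyses it lists "generalized linear models with scale factor estimation to account for under- or over-dispersion", and for counts it names "count endpoint data (dispersion-corrected negative binomial regression").

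The same section says that each of the 16 secondary endpoints will be "compared across the 3 vitamin E doses vs Placebo using treatment effect estimates, 95% confidence limits, and p-values", and that the Benjamini-Hochberg method will "adjust the presented p-values for the false discovery rate (FDR) from the 16x3=48 pairwise p-values". No sentence says what happens if the Poisson and dispersion-corrected results disagree.

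The relevant item in the list in 9.1 is "Change in frequency of CTCAE defined adverse events from baseline to 24 weeks". Section 9.4.4 adds patient-level adverse-event tables (any event, number of events, highest severity), which "will be displayed by treatment group along with p-values from Fisher's exact tests".

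**The concern.** A Poisson model with its own model-based variance takes the variance of each patient's count to equal its mean. Some patients may be more prone than others to have or report adverse events. If so, the variance exceeds the mean, and the model gives standard errors that are too small, confidence limits that are too narrow and p-values that are too low. Section 9.4.3 foresees this possibility, but it takes the headline estimates, limits and p-values from the model that does not allow for it.

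At stake is the adverse-event row of the secondary table. A dose could be reported as raising or lowering adverse events when it does neither, or its rate ratio could be shown with unwarranted precision. With two planned models and no rule between them, the choice could also be made after the results are seen.

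**Working it through.** **Which endpoint is a count.** The list in 9.1 has 16 items, which matches the plan's 16 x 3 = 48 comparisons. ALT normalization is binary. The rest are changes in or time courses of laboratory, imaging, anthropometric or symptom measures, except the frequency of adverse events. If that item is not the count, the Poisson sentence applies to nothing. This is a strong inference, not stated text.

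**Inputs from the documents.** 50 patients per group and four groups (9.2); three comparisons with placebo per endpoint and 48 p-values in the Benjamini-Hochberg family (9.4.3).

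**Inputs that are assumed.** The documents give no adverse-event rate, no dispersion and no false-positive rate for this endpoint, so there is no planned figure to reproduce. The check assumes 0.5 to 3 events per patient on average, the same mean in all arms, gamma-Poisson (negative binomial) counts, and a variance/mean ratio φ from 1 upward. Raw and adjusted p-values are both read at 5%; the plan states no level for the FDR.

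**Formula.** For total counts S1 (dose) and S0 (placebo) in equal arms, the Poisson Wald statistic is

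z = ln(S1/S0) / √(1/S1 + 1/S0).

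If the variance is φ times the mean, the true variance of ln(S1/S0) is about φ(1/S1 + 1/S0). Then z has standard deviation √φ instead of 1, and

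size = 2[1 − Φ(1.96/√φ)], coverage of the nominal 95% interval = 1 − size.

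For φ = 2: 1.96/√2 = 1.386, so size = 16.6% and coverage = 83.4%.

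**Simulation.** 40,000 trials per setting, four arms of 50, no dose effect. For the adjusted columns, the three Poisson p-values were put into a 48-test family with 45 independent null p-values.

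| φ | Size, formula | Coverage, formula | Size, simulated | After adjustment, per comparison | After adjustment, any of three doses |
|---|---|---|---|---|---|
| 1 | 5.0% | 95.0% | 5.0% | 0.1% | 0.3% |
| 1.1 | 6.2% | 93.8% | – | – | – |
| 1.25 | 8.0% | 92.0% | 7.6% | 0.3% | 0.8% |
| 1.5 | 11.0% | 89.0% | 10.8% | 0.8% | 2.0% |
| 2 | 16.6% | 83.4% | 16.2% | 2.1% | 5.1% |
| 3 | 25.8% | 74.2% | 25.4% | 6.2% | 14.1% |

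Simulated values are at a mean of 2 events per patient, except φ = 1.25, which is at a mean of 1.

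**Sensitivity of the adjusted rates.** They depend on the other endpoints. At φ = 2, with 5 clearly significant p-values elsewhere in the family, the adjusted rate is about 5.1% per comparison; with 15 it is about 8.9%. True Poisson counts give about 0.6% and 1.5%.

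**Does a correction work?** With a Pearson scale factor pooled over the four arms, the unadjusted size was 4.6% to 5.2% in every setting, φ from 1 to 5.5. The planned negative binomial model was not fitted in this check.

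**The case against.** The strongest reply is that the plan has already dealt with this. The dispersion-corrected model is in the same paragraph and will be run anyway, so only the labels main and sensitivity are in dispute. That stands in part: a reader could not fairly say that over-dispersion was overlooked. But the labels decide which limits and p-values enter the table and the FDR family, and nothing settles a disagreement.

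Four stronger readings are tempting, and the documents do not support them.

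- *The test has two to five times its nominal error.* That needs φ between about 1.42 and 2.90, and no section gives a dispersion. At 1.1 to 1.25 the factor is 1.2 to 1.6; at 4 it is 6.5. It also describes unadjusted p-values, whereas the plan presents adjusted ones.
- *The plan itself expects clustering, because 9.4.4 tabulates* "frequency of multiple adverse events (i.e., 0, 1, 2, 3" *or more).* These are table categories. A pure Poisson count with mean 1 already puts about 37%, 37%, 18% and 8% of patients in them.
- *The small p-values distort the other secondary endpoints.* Three extra rejections raise the step-up threshold by at most 3 x 0.05/48 = 0.003. At φ = 3 and a mean of 1.5, the chance of any false finding among 45 null tests rises only from 4.7% to 5.7%.
- *The safety conclusions of the trial are compromised.* The Fisher tests in 9.4.4 count each patient once, so repeated events do not inflate them. They do not, however, replace the frequency estimate and interval in the secondary table.

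**Conclusion.** The point holds as a modest, cheaply corrected weakness in one of 16 secondary endpoints. If the adverse-event endpoint is the count that 9.4.3 has in mind, and if events cluster within patients, the main-table limits are too narrow and the p-values entering the FDR family are too small.

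The direction is certain under over-dispersion. The size is conditional: negligible at φ near 1, material from about 1.5, where nominal 95% limits cover about 89%, and substantial at 2 to 3. Multiplicity adjustment keeps the presented p-values below 5% per comparison up to φ of about 2.5 when everything else is null, but still well above the rate with a correct variance. It does nothing for the confidence limits. The minimum-effective-dose decision on ALT does not depend on any of this.

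**What to change.** In 9.4.3, name one dispersion-corrected model as the main analysis for counts: for example the negative binomial regression already planned, or Poisson regression with a Pearson scale factor. State that its estimates, 95% limits and p-values go into the secondary table and the Benjamini-Hochberg family, and move plain Poisson to the sensitivity list. In the same sentence, say that the adverse-event frequency endpoint is the count to which this applies.

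The cost is a sentence or two of text. No new data, patients or models are needed. The downside is wider intervals when events are over-dispersed: on the log scale by a factor of √φ, that is 1.22, 1.41 and 1.73 at φ = 1.5, 2 and 3. When the counts are truly Poisson, the scaled model kept its error rate close to 5% in simulation.

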- Any other condition which, in the opinion of the investigator, would impede compliance or hinder completion of the study, including inability to swallow treatment capsules
- Failure or inability to give informed consent

Sample size / Power:

- Total sample size = 200; 50 per group
- Power = 90%
- Type I error (2-sided) = 5%
- Increase in sample size due to missing data = 10%
- Mean (SD) difference (Vitamin E – Placebo) in relative change [(BL-FU)/BL] in ALT at 24 weeks = 20% (31%)
 - Mean relative change (%) in ALT at 24 weeks in placebo = 20% (based on data from PIVENS trial)
 - Mean relative change (%) in ALT at 24 weeks in Vitamin E = 40% (based on data from PIVENS trial)
- Method of analysis = Williams' test for minimum effective dose

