7.2 PARTICIPANT DISCONTINUATION/WITHDRAWAL FROM THE STUDY

Participants are free to withdraw from participation in the study at any time upon request.

An investigator may discontinue or withdraw a participant from the study for the following reasons:

- Pregnancy
- Significant study intervention non-compliance (as determined by primary investigator)
- If any clinical adverse event (AE), laboratory abnormality, or other medical condition or situation occurs such that continued participation in the study would not be in the best interest of the participant
- Disease progression which requires discontinuation of the study intervention
- If the participant meets an exclusion criterion (either newly developed or not previously recognized) that precludes further study participation
- Participant unable to receive study drug for > 4 weeks.

Discontinuation from the study medication (vitamin E or matching placebo) does not mean discontinuation from the study and remaining study procedures should be completed as indicated by the study protocol. The reason for participant discontinuation or withdrawal from the study will be recorded on the Case Report Form (CRF). Participants who sign the informed consent form and are registered but do not receive the study intervention may be replaced. Participants who sign the informed consent form, and are randomized and receive the study intervention, and subsequently withdraw, or are withdrawn or discontinued from the study will not be replaced.

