9.3 POPULATIONS FOR ANALYSES

The analysis dataset will include:

- Intention-to-Treat (ITT) Analysis Dataset (i.e., all randomized participants)
- Safety Analysis Dataset: defines the subset of participants for whom safety analyses will be conducted (e.g., participants who took at least one dose of study intervention)
- Other Datasets that may be used for sensitivity analyses (e.g. subgroups by dose, sex, age, baseline labs, adherence)

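### Section 9.4.3 gives the 24-week adverse-event count no follow-up-time term and no definition of complete data, so participants who leave the study early are not properly handled

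*Combined protocol and SAP*

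**What the plan says.** Sections 3 and 9.1 list the endpoint as "Change in frequency of CTCAE defined adverse events from baseline to 24 weeks". I read it as the number of events over the 24 weeks after baseline; its wording as a change is a separate matter.

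Section 9.4.3 specifies "logistic regression for binary endpoints, and Poisson regression for counts". No offset, person-time or rate appears there, nor in the safety analyses of 9.4.4.

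Section 9.4.3 states the analysis set twice. A bullet, without condition, restricts secondary analyses to "all randomized participants with complete data on each specific secondary endpoint". The paragraph below makes this conditional: "Complete case analyses will be used for each secondary endpoint, if missing data on that endpoint < 10" per cent, whereas "multiple imputation will be used if missing data on the secondary endpoint is 10% or greater". It does not say whether the percentage is pooled or taken by arm, or what makes an event count complete.

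Section 9.3 defines a Safety Analysis Dataset, for example "participants who took at least one dose of study intervention", but 9.4.3 does not use it for this endpoint.

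Sections 7.1 and 7.2 keep participants who stop the drug in follow-up. Section 7.2 also lets the investigator withdraw a participant from the study when an adverse event means that "continued participation in the study would not be in the best interest of the participant", and 7.3 covers loss to follow-up.

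**The concern.** A participant who leaves at week 6 has a six-week count. The plan does not say whether that count is complete. If it is not, the participant is excluded, or their 24-week count is imputed, even though their events and time at risk up to week 6 are known. If it is, a Poisson model without an offset treats six weeks as 24.

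For a safety count, leaving may itself follow from an event. If drug-related events lead to study withdrawal more often than background events do, the dose-versus-placebo ratio moves toward no harm. The trial's rationale (2.3.3) is that a lower dose may avoid long-term adverse effects, and this ratio is reported for each of the three doses in the secondary table.

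**Working it through.** **Inputs from the documents.** There are 50 participants per arm (9.2). No adverse-event rate, withdrawal rate or power is given for this endpoint, so there is no planned figure to reproduce. All rates below are assumptions.

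**Setting A: leaving is triggered by events.** Take 24 weeks as the time unit, a background rate of 1.0 and 0.5 added by the drug, so the true ratio is 1.50. Each background event leads to leaving the study with probability b, and each drug-related event with probability d. The leaving hazards are h0 = b on placebo and h1 = b + 0.5d on drug, and the share leaving is 1 − exp(−h).

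- Completers contribute only events that did not trigger leaving: ratio = 1 + 0.5(1 − d)/(1 − b).
- Without an offset, the mean count is the rate times the mean time observed, m(h) = (1 − exp(−h))/h: ratio = 1.5 × m(h1)/m(h0).
- With an offset, events per unit of time give 1.50, because the rate is constant.

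| b, d | Leaving, placebo / drug | Completers | No offset |
|---|---|---|---|
| 7%, 20% | 6.8% / 15.6% | 1 + 0.5×0.80/0.93 = 1.43 | 1.5×0.9196/0.9658 = 1.43 |
| 7%, 30% | 6.8% / 19.7% | 1 + 0.5×0.70/0.93 = 1.38 | 1.5×0.8976/0.9658 = 1.39 |
| 5%, 40% | 4.9% / 22.1% | 1 + 0.5×0.60/0.95 = 1.32 | 1.5×0.8848/0.9754 = 1.36 |

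Simulations with 50 per arm agree: completers 1.43, 1.38 and 1.31-1.32; no offset 1.43, 1.39 and 1.36; with offset about 1.50.

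If b = d = 20%, completers give 1 + 0.5×0.80/0.80 = 1.50, which is unbiased. Without an offset the ratio is still 1.5×0.8639/0.9063 = 1.43.

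**Which branch of 9.4.3 applies.** If the percentage is pooled and only one dose carries the effect, missingness in the three rows is (3×6.8 + 15.6)/4 = 9.0%, (3×6.8 + 19.7)/4 = 10.0% and (3×4.9 + 22.1)/4 = 9.2%, which is at the threshold. If all three doses carry it, the figures are (6.8 + 3×15.6)/4 = 13.4%, 16.5% and 17.8%, and imputation applies.

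**Setting B: a fixed share q leaves, each at the first event.** With mean λ and g = λ/(1 − exp(−λ)), the mean count without an offset is λ − q(g − 1), and the completers' mean is (λ − qg)/(1 − q). Take q = 5% on placebo and 15% on one dose, true ratio 1.50. If the other arms lose 5%, pooled missingness is (3×5 + 15)/4 = 7.5%, so complete case applies.

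| Placebo mean | No offset | Completers |
|---|---|---|
| 1 | 1.3604/0.9709 = 1.40 | 1.4240/0.9694 = 1.47 |
| 2 | 2.6764/1.9343 = 1.38 | 2.9723/1.9835 = 1.50 |
| 3 | 3.9674/2.8921 = 1.37 | 4.4911/2.9917 = 1.50 |

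Simulation gives 1.39, 1.38 and 1.37 without an offset, 1.46, 1.50 and 1.50 for completers, and 1.49-1.50 with an offset.

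**Balanced leaving.** With q = 5% in both arms and placebo mean 1, no offset gives 1.4535/0.9709 = 1.50 and completers 1.4773/0.9694 = 1.52. The bias is about 2% or less in all the balanced cases run.

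**The case against.** Several stronger readings are tempting, and the documents do not support them.

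- **Early leavers are always dropped.** Section 9.4.3 switches to multiple imputation at 10% or more missing, and several assumed settings above reach that point. Exclusion, or reading a short count as a full one, follows from the plan's silence; neither is a stated rule.
- **The plan expects 10% of participants to leave.** The synopsis entry "Increase in sample size due to missing data = 10" per cent is, as 9.2 shows, an allowance for missing primary ALT data. It is not a withdrawal rate, still less a rate of withdrawal for adverse events.
- **Anyone taken off the drug for an adverse event is lost.** Sections 7.1 and 7.2 keep them in follow-up. Withdrawal from the study for an adverse event is discretionary, and the 20-40% per drug-related event in Setting A has no basis in the documents.
- **Leavers' events vanish.** Under 8.3.4, events are recorded with onset until 7 days (30 for serious events) after the last day of participation, and 9.4.4 lists and tabulates events by arm.

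The bias is also modest beside the sampling error. With 50 and 75 expected events, the standard error of the log ratio is √(1/50 + 1/75) = 0.18, against a bias of ln(1.50/1.43) = 0.05 to ln(1.50/1.31) = 0.14.

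These points narrow the concern without closing it. The 9.4.4 tables do not adjust for time at risk and do not correct the ratio in the secondary table. The planned negative binomial sensitivity analysis addresses dispersion, and no offset is named for it. Imputation would replace time and events that were actually observed.

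**Conclusion.** The point holds in a limited form. For the adverse-event count, 9.4.3 names no follow-up-time term, does not define complete data, and states the complete-case rule once without condition and once with it. Only participants who leave the study before week 24 are affected.

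Under assumed unequal leaving (about 5-7% against 15-22%), a true ratio of 1.50 becomes about 1.36-1.43 without an offset and about 1.31-1.50 in complete cases. The result depends on how leaving relates to events: complete-case bias can be nil or the larger of the two. With low, balanced leaving it is negligible. All of this rests on assumed event and withdrawal rates, and the documents do not show that leaving will be unequal. The change is worth making because the better analysis is nearly free.

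**What to change.** For this endpoint, replace the complete-case and imputation rule in 9.4.3 with wording such as: all participants in the Safety Analysis Dataset are included; all adverse events are counted from first dose through the earlier of week 24 and end of study follow-up, whether or not the participant is still taking the drug; counts are compared by Poisson or negative binomial regression with an offset of log follow-up time over that same period. Events and time must cover the same window: counting only on-treatment events against time that includes off-drug follow-up would lower the rate in arms with more drug stopping. For the other secondary endpoints, reconcile the unconditional complete-case bullet with the 10% rule.

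The cost is one sentence and one model term, settled before unmasking. Event onset (8.3.4) and time since randomization (9.4.4) are already recorded. If the date of first dose is not captured, the randomization date can start both the count and the clock.

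The small downside is that the offset assumes a roughly constant event rate and does not fully remove bias if leaving depends on unmeasured frailty. Adding gamma heterogeneity (assumed dispersion 1) to Setting A gives about 1.37-1.43 with person-time, although complete case is worse there, at about 1.09-1.30.
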